7.14 Efficacy

Primary efficacy variable: The primary objective of this study is to evaluate the efficacy of Ra-223 based on bone scan response measured by quantitative analysis of ^{99m}Tc -MDP bone scan. The bone scan area that we will employ for analysis was developed as a quantitative tool to improve the interpretability and clinical relevance of the bone scan. The BSA is a method of expressing the tumor burden in bone as a percent of the total skeletal mass. For analysis, scan images are intensity normalized, and the lesions are identified and segmented by anatomic region-specific intensity thresholding, and area summed (resulting in a bone scan area measurement for the skeleton and lesions). This calculated ratio of lesion area to bone scan area (calculated from two dimensional planar images) will be used to assess percent change with treatment. Bone scan response is defined as a $\geq 30\%$ decrease in quantitative bone scan lesion area (BSA) from baseline to the end of month 2 of Ra-223 treatment (i.e. after the second of six possible Ra-223 doses).

Secondary variables: Please see statistical methods in protocol Section 8.

7.15 Safety

The sponsor is responsible to comply with the local regulation and legislation for adverse events reporting.

All subjects who receive at least one dose of study treatment will be valid for the safety analysis.

All observations pertinent to the safety of the study treatment will be recorded and included in the final report.

All AEs whether considered drug-related or not, will be reported with a diagnosis, start/stop dates, action taken, whether treatment was discontinued, any corrective measures taken, outcome, and other possible causes. For all events, the relationship to treatment and the intensity of the event will be determined by the investigator.

This trial will use the NCI-CTCAE v4.0 criteria for assessment of toxicity and SAE reporting with regard to toxicity grade.

Safety variables may include but not limited to the following: laboratory changes (complete blood counts, electrolytes, chemistry, and coagulation), changes in vital signs (blood pressure, heart rate, respiratory rate, and temperature) and ECG and, in some instances, changes in chest x-ray images, as produced at the investigator's discretion (e.g., for evaluation for pneumonia).

7.15.1 Adverse events

Investigators should refer to the Safety Information section of the current IB for Ra 223 dichloride, including the DCSI (development core safety information), for the expected side effects of Ra 223 dichloride. As with any agent, there is always the potential for unexpected AEs, including hypersensitivity reactions. The IB will be updated if any new relevant safety data are obtained.

Therapeutic monitoring should be performed following dose selection of Ra 223 dichloride in a manner consistent with the local clinical standard of care. In general, subjects should be closely monitored for side effects of all concomitant medications regardless of the path of drug elimination.

All concomitant medications must be recorded in the subject's source documentation.

Subjects must be carefully monitored for AEs. This monitoring also includes clinical laboratory tests. Adverse events should be assessed in terms of their seriousness, intensity, and relationship to the study drug, or other chemotherapy/treatment.

7.15.1.1 Definitions

Definition of adverse event (AE)

In a clinical study, an AE is any untoward medical occurrence (i.e. any unfavorable and unintended sign [including abnormal laboratory findings], symptom or disease) in a patient or clinical investigation subject after providing written informed consent for participation in the study. Therefore, an AE may or may not be temporally or causally associated with the use of a medicinal (investigational) product.

A surgical procedure that was planned prior to the start of the study by any physician treating the subject should not be recorded as AE (however, the condition for which the surgery is required may be an AE if the condition worsens compared to baseline).

- Conditions that started before signing of informed consent and for which no symptoms or treatment are present until signing of informed consent are recorded as medical history (e.g. seasonal allergy without acute complaints).
- Conditions that started before signing of informed consent and for which symptoms or treatment are present after signing of informed consent, at *unchanged intensity*, are recorded as medical history (e.g. allergic pollinosis).
- Conditions that started or deteriorated after signing of informed consent will be documented as adverse events.

Definition of serious adverse event (SAE)

An SAE is classified as any untoward medical occurrence that, at any dose, meets any of the following criteria (a – f):

- a. Results in death.
- b. Is life-threatening.

The term 'life-threatening' in the definition refers to an event in which the patient was at risk of death at the time of the event, it does not refer to an event which hypothetically might have caused death if it were more severe.

- c. Requires inpatient hospitalization or prolongation of existing hospitalization.

A hospitalization or prolongation of hospitalization will not be regarded as an SAE if at least one of the following exceptions is met:

- The admission results in a hospital stay of less than 12 hours.
- The admission is pre-planned.
(i.e. elective or scheduled surgery arranged prior to the start of the study)
- The admission is not associated with an AE.
(e.g. social hospitalization for purposes of respite care).

However, it should be noted that invasive treatment during any hospitalization may fulfill the criterion of 'medically important' and as such may be reportable as an SAE

dependent on clinical judgment. In addition, where local regulatory authorities specifically require a more stringent definition, the local regulation takes precedence.

- d. Results in persistent or significant disability / incapacity.

Disability means a substantial disruption of a person's ability to conduct normal life's functions.

- e. Is a congenital anomaly / birth defect.
- f. Is another medically important serious event as judged by the investigator.

7.15.1.2 Classifications for adverse event assessment

All AEs will be assessed and documented by the investigator according to the categories detailed below.

7.15.1.2.1 Seriousness

For each AE, the seriousness must be determined according to the criteria given in Section 7.15.1.1.

7.15.1.2.2 Intensity

The intensity of the AE is classified according to the CTCAEv4.0. Grade refers to the severity (intensity) of the AE:

CTCAEv4 Grade 1: mild; asymptomatic or mild symptoms; clinical or diagnostic observations only; intervention is not indicated.

CTCAEv4 Grade 2: moderate; minimal, local, or noninvasive intervention is indicated; limiting to age-appropriate instrumental activities of daily living (ADL; instrumental ADL refers to preparing meals, shopping for groceries or clothes, using the telephone, managing money, etc).

CTCAEv4 Grade 3: Severe or medically significant but not immediately life threatening; hospitalization or prolongation of hospitalization is indicated; disabling; limiting to self care ADL (self care ADL refers to bathing, dressing and undressing, feeding self, using the toilet, taking medications, and not bedridden).

CTCAEv4 Grade 4: life-threatening consequences; urgent intervention is indicated.

CTCAEv4 Grade 5: death due to an AE.

7.15.1.2.3 Causal relationship

The assessment of the causal relationship between an AE and the administration of treatment is a clinical decision based on all available information.

The assessment is based on the question whether there was a "reasonable causal relationship" to the study treatment in question.

Possible answers are "yes" or "no".

An assessment of "no" would include:

"The values in this protocol have been revised as per the United States (US) National Institute of Standards and Technology (NIST) standardization update (agreed on 17 MAR 2015)"

1. The existence of a clear alternative explanation, e.g. mechanical bleeding at surgical site.
- or
2. Non-plausibility, e.g. the subject is struck by an automobile when there is no indication that the drug caused disorientation that may have caused the event; cancer developing a few days after the first drug administration.

An assessment of “yes” indicates that there is a reasonable suspicion that the AE is associated with the use of the study treatment.

Factors to be considered in assessing the relationship of the AE to study treatment include:

- The temporal sequence from drug administration: The event should occur after the drug is given. The length of time from drug exposure to event should be evaluated in the clinical context of the event.
- Recovery on drug discontinuation (de-challenge), recurrence on drug re-introduction (re-challenge):
- Subject’s response after de-challenge or subjects response after re-challenge should be considered in the view of the usual clinical course of the event in question.
- Underlying, concomitant, intercurrent diseases:
Each event should be evaluated in the context of the natural history and course of the disease being treated and any other disease the subject may have.
- Concomitant medication or treatment:
The other drugs the subject is taking or the treatment the subject receives should be examined to determine whether any of them may be suspected to cause the event in question.
- The pharmacology and pharmacokinetics of the study treatment:
The pharmacokinetic properties (absorption, distribution, metabolism and excretion) of the study treatment, coupled with the individual subject’s pharmacodynamics should be considered.

Causal relationship to protocol-required procedure(s)

The assessment of a possible causal relationship between the AE and protocol-required procedure(s) is based on the question whether there was a “reasonable causal relationship” to protocol-required procedure(s).

Possible answers are “yes” or “no”.

7.15.1.2.4 Action taken with study treatment

Any action on study treatment to resolve the AE is to be documented using the categories listed below.

- Drug withdrawn
- Drug interrupted
- Dose not changed
- Dose increased
- Not applicable
- Unknown

7.15.1.2.5 Other specific treatment(s) of adverse events

- None
- Remedial drug therapy
- Other

7.15.1.2.6 Outcome

The outcome of the AE is to be documented as follows:

- Recovered/resolved
- Recovering/resolving
- Recovered/resolved with sequelae
- Not recovered/not resolved
- Fatal
- Unknown

7.15.1.3 Assessments and documentation of adverse events

7.15.1.4 Reporting of serious adverse events

The definition of serious adverse events (SAEs) is given in Section 7.15.1.1.

Each serious adverse event must be followed up until resolution or stabilization, by submission of updated reports to the designated person. An isolated laboratory abnormality that is assigned grade 4, according to CTC definition, is not reportable as an SAE; unless the investigator assesses that the event meets standard ICH criteria for an SAE. CTC grade 4 baseline laboratory abnormalities that are part of the disease profile should not be reported as an SAE, specifically when they are allowed or not excluded by the protocol inclusion/exclusion criteria.

When required, and according to local law and regulations, serious adverse events must be reported to the Ethics Committee and Regulatory Authorities.

All serious adverse events should be reported to Bayer within 24 hours. In the event of such an event, the investigator should refer to the Pharmacovigilance section of the contract for reporting procedures.

Requirements for Reporting of Serious Adverse Events:

All SAEs must be reported to Bayer within 24 hours of the Principal Investigator's awareness and must include the following minimum information:

1. The name and contact information of the reporter
2. The name of the study drug(s)
3. A description of the reported SAE
4. A patient identified by one or more of the following:
 - a. Patient initials
 - b. Patient number
 - c. Knowledge that a patient who experienced the adverse event exists
 - d. Age
 - e. Sex
5. An investigator assessment of study drug causality. For studies with combination therapy, a separate causality assessment should be provided for each study drug.

Additional data which would aid the review and causality assessment of the case include but are not limited to:

The date of onset

The severity

The time from administration of study drug(s) to start of the event

The duration and outcome of the event

Any possible etiology for the event

The final diagnosis or syndrome, if known

The Investigator may report serious adverse drug reactions (SADRs) using either:

An ADEERS form (Adverse Event Expedited Reporting System) available at

<http://ctep.cancer.gov/reporting/adeers.html>

OR

A MedWatch form available at <http://www.fda.gov/medwatch/>

All reports shall be sent electronically to:

Electronic Mailbox: [contact]

[contact]

7.15.1.5 Expected adverse events

For this study, the applicable reference document is the most current version of the investigator's brochure (IB) / summary of product characteristics.

The expectedness of AEs will be determined by Bayer according to the applicable reference document and according to all local regulations.

7.15.2 Pregnancies

The investigator must report to Bayer any pregnancy occurring in a study subject's partner, during the subject's participation in this study. The report should be submitted within the same timelines as an SAE, although a pregnancy per se is not considered an SAE. For the pregnancy of a study subject's partner, all efforts should be made to obtain information on course and outcome, subject to the partner's consent. For all reports, the forms provided are to be used.

7.15.3 Further safety

Progressive disease

If progressive disease leads to signs and symptoms that meet the criteria for an SAE (i.e., hospitalization, disability, death, or important medical event), the signs and symptoms should be reported as an SAE and not the underlying progressive disease.

Death

If any subject dies during the trial or within 30 days of the end-of-treatment visit, the investigator will inform Bayer and record the cause of death in detail (using the SAE Form) within 24 hours.

7.16 Other procedures and variables

7.17 Appropriateness of procedures / measurements

The assessments described in the previous sections are widely used and generally recognized as reliable, accurate, and relevant for determining the safety and efficacy of therapies in this disease.

8. Statistical methods and determination of sample size

Primary Aim

“The values in this protocol have been revised as per the United States (US) National Institute of Standards and Technology (NIST) standardization update (agreed on 17 MAR 2015)”

Bone scan response is defined as a $\geq 30\%$ decrease in quantitative bone scan lesion area (BSA) from baseline to the end of month 2 of Ra-223 treatment (i.e. after 2 of 6 possible Ra-223 doses). In a one-stage design, 22 subjects will be enrolled to evaluate the primary endpoint of bone scan response. Assuming 90% of subjects with adequate data, the evaluable sample size is 20 subjects. With 20 subjects, given target power of 90% and 1-sided 5% alpha, a null hypothesis of $\leq 10\%$ versus an alternative hypothesis of $\geq 35\%$ in the proportion of patients achieving response can be evaluated. If 5 or more responses are observed in 20 subjects, this method of response assessment will be considered promising.

Operating characteristics

Probability of ≥ 5 responses in 20 pts	True but unknown rate of Bone Scan Response Rate					
	10%	15%	20%	25%	30%	35%
Probability of ≥ 5 responses in 20 pts	0.04	0.17	0.37	0.59	0.76	0.88

Secondary Aims

A key secondary objective is to evaluate whether quantitative analysis of ^{99m}Tc -MDP bone scan after 2 months of therapy can identify patients who will achieve long term clinical benefit. Towards this end, all subjects will be treated and followed for at least 18 months. Survival status at 18 months will be ascertained (i.e. dichotomized as survivor or non-survivor at 18 months). A two-sample t-test will be used to determine the difference in mean percent change in BSA between survivor and non-survivor groups. Reported median survival for the study cohort of the ALSYMPCA trial was 14.9 months. Assuming events follow an exponential distribution this parallels an 18-month survival rate of 43%. The detectable difference will depend on the variability in change in BSA as measured by standard deviation (SD). There is 80% power to detect an effect of 1.332 SD given a 2-sided 0.05 alpha and 20 evaluable patients divided as 9 survivors and 11 non-survivors.

Bone scans are scheduled for the beginning of month 3/end of month 2 (T3), and one month post month 6 (FU1M). Descriptive statistics on absolute and percent change in BSA from baseline to these study timepoints will be provided for the overall study cohort and within survivor groups. By the end of month 2, bone scan response is expected in 35% of subjects. Patients will be cross-classified by bone scan response status at 2 months and survival status at 18 months. Agreement will be quantified using Cohen's Kappa; however, the sample size is too small to produce a realistic confidence interval. Kappa is assessed as follows: <0.00, poor; 0.00-0.20, slight; 0.21-0.40, fair; 0.41-0.60, moderate; 0.61-0.80, substantial; 0.81-1.00, almost perfect; and 1.00, perfect. Survival time defined as the time from registration to death, or if censored to date last known alive will be calculated. Correlation between change in BSA after 2 months and survival time will be assessed graphically with scatter plots and using Pearson correlation coefficient. Survival distributions will also be estimated using the Kaplan-Meier method in a landmark analysis at 2 months. Survival time is defined as the time from response classification (at 2 months) to death, or if censored to date last known alive. Cox proportional hazards (PH) regression will be used to estimate the bone scan response hazard ratio along with 95% confidence limits.

This study also affords insights into several other potential biomarkers including measures related to circulating tumor cells (number, proliferative index, AR signaling, markers of DNA damage/repair), bone turnover (BAP, NTx), inflammation and angiogenesis. Fluciclovine PET imaging will occur in 10 subjects at baseline and the end of month 2 of treatment. All other measures will occur at baseline, during treatment, and post treatment as detailed in the required data table. Descriptive statistics will be provided for each measure and timepoint along with absolute and percentage change from baseline. Association with overall survival and response will be analyzed as exploratory similar to the methods above for bone scan.

Accrual Targets

Accrual Targets						
Ethnic Category	Sex/Gender					
	Females		Males		Total	
Hispanic or Latino	0	+	1	=	1	
Not Hispanic or Latino	0	+	21	=	21	
Ethnic Category: Total of all subjects	0	(A1)	+	22	(B1) = 22 (C1)	
Racial Category						
American Indian or Alaskan Native	0	+	0	=	0	
Asian	0	+	1	=	1	
Black or African American	0	+	1	=	1	
Native Hawaiian or other Pacific Islander	0	+	0	=	0	
White	0	+	20	=	20	
Racial Category: Total of all subjects	0	(A2)	+	22	(B2) = 22 (C2)	
	(A1 = A2)		(B1 = B2)		(C1 = C2)	

Timeline

We anticipate an average of 2 subjects to be accrued monthly (approximate accrual time: 12 months). The primary endpoint (assessment of change in total area of bone metastases by ^{99m}Tc MDP bone scan) is assessed 2 months after the start of treatment; the primary analysis will take place 14 months after study activation. With an anticipated 12 month enrollment period and per-subject 18 months of study-directed treatment and follow-up, the last enrolled patient will conclude follow-up 30 months after activation.

Notable anticipated dates and analyses are as follows:

- T: 0m Study opens for accrual at MGH
- T: 12m Study accrual completed
- T: 14m Primary analysis
- T: 30m Completion of all study follow-up

9. Data handling and quality assurance

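### Does Section 8 need a rule for men who die or are lost before the month-2 scan?

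*Combined protocol and SAP*

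**What the plan says.** The Primary Aim in Section 8 (repeated in the synopsis) enrols 22 men and states: "Assuming 90% of subjects with adequate data, the evaluable sample size is 20 subjects". It tests a null of at most 10% against an alternative of at least 35% "in the proportion of patients achieving response can be evaluated", at one-sided 5% alpha with 90% target power. The decision rule is a count: "If 5 or more responses are observed in 20 subjects, this method of response assessment will be considered promising". Response is a fall of at least 30% in lesion area from baseline to the end of month 2 (Sections 7.14 and 8). Under Section 7.1.1, note 1, the scan falls within 10 days before the third dose.

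The Secondary Aims give a survival model: "Reported median survival for the study cohort of the ALSYMPCA trial was 14.9 months" and "Assuming events follow an exponential distribution this parallels an 18-month survival rate of 43"%. They add: "Patients will be cross-classified by bone scan response status at 2 months and survival status at 18 months", with agreement scored by kappa against printed verbal bands. The expected margin is also given: "By the end of month 2, bone scan response is expected in 35% of subjects". For time to death: "Survival distributions will also be estimated using the Kaplan-Meier method in a landmark analysis at 2 months".

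The only analysis set defined by name is the safety set (Section 7.15). Withdrawn subjects are not replaced (Section 5.2.5).

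**The concern.** The hypothesis is about patients, while the sizing and the count are about evaluable subjects, a term left undefined. A man who dies, withdraws or is lost after dose one but before the scan has no stated place. Such gaps are not random: none of these men can be an observed responder, and every pre-scan death is an 18-month non-survivor.

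Two results seem exposed. First, if exactly five men respond and two are unscanned, an exact 5% test passes on 20 and fails on 22. Second, entering two pre-scan deaths in the kappa table as non-responders adds two automatic agreements, which could lift the verbal label although the scan predicted nothing. The section declines a confidence interval for kappa, so the label carries the interpretation.

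**Working it through.** **Inputs.** From Section 8: 22 enrolled, 20 evaluable, null 10%, alternative 35%, cut-off 5, median survival 14.9 months with exponential times, 9 survivors and 11 non-survivors, 35% expected response (7 of 20). From Section 7.1.1: third dose at day 56 ± 7, scan up to 10 days earlier.

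**Plan's own figures.** P(X ≥ 5 | n = 20) at 10, 15, 20, 25, 30 and 35% is 0.0432, 0.170, 0.370, 0.585, 0.763 and 0.882. The printed row is 0.04, 0.17, 0.37, 0.59, 0.76 and 0.88, so it is right. S(18) = 0.5^(18/14.9) = 0.433, matching the plan's 43%.

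**Deaths before the scan.** Expected number = 22 × (1 − 0.5^(t/14.9)).

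| Time | Proportion dead | Deaths of 22 |
|---|---|---|
| day 39 (dose 3 a week early, scan 10 days before) | 5.8% | 1.27 |
| day 46 | 6.8% | 1.49 |
| day 56 | 8.2% | 1.80 |
| 2 months | 8.9% | 1.95 |

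The 90% assumption allows 22 × 0.10 = 2.2. Half the hazard gives 0.76 at day 46 and 1.0 at 2 months.

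**Cut-off by denominator.** At a 10% rate, P(X ≥ 5) is 0.028 at n = 18, 0.035 at 19, 0.043 at 20, 0.052 at 21 and 0.062 at 22. A re-derived exact 5% test therefore keeps 5 for 15 to 20 subjects and needs 6 at 21 or 22. If that test replaced the printed count, excluding the unscanned and counting them as non-responders would disagree when exactly five respond and at least two are unscanned. With 90% evaluability that has probability Σ Bin(n; 22, 0.9) × P(X = 5 | n, p) over n = 15 to 20, which is 1.8%, 13.2% and 9.6% at p = 10, 25 and 35%.

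**The rule as printed.** An unscanned man cannot respond, so the number of responders among the scanned equals the number among all treated. Five or more is one event under both countings:

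Σ Bin(n; 22, e) × P(X ≥ 5 | n, p) = P(Bin(22, e·p) ≥ 5), where e is the proportion scanned.

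At p = 35%:

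- e = 0.911 (deaths to 2 months only): 0.878
- e = 0.911 × 0.95 = 0.866: 0.843
- e = 0.911 × 0.90 = 0.820: 0.801

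The extra 5% and 10% losses are assumptions; the documents give no such rate. If 10% is the rate among the scanned, error at e = 0.911 is 4.4%. If 10% is the rate among all treated, error is 6.2%. Each figure is the same under either counting.

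**Kappa.** Take the plan's margins with 5 responder-survivors: cells (5, 2, 4, 9). Observed agreement is 14/20 = 0.700, chance agreement is (7×9 + 13×11)/400 = 0.515, and kappa = 0.185/0.485 = 0.381. Adding two deaths to the last cell gives 16/22 = 0.727 and (7×9 + 15×13)/484 = 0.533, so kappa = 0.416, and fair becomes moderate.

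I then enumerated every table with the 9/11 split and added two deaths. From 3 to 10 responders, the label changes only at 7 (5 of 8 tables) and at 9 (5 of 10); at 3 to 6, 8 and 10 it never changes. At 7 responders, one added death changes it in 1 of 8. With five responders, the only count at which the verdict could turn, kappa moves from 0.158 to 0.193, 0.368 to 0.394 or 0.579 to 0.596, all within a band.

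**The case for a change.** The strongest case for a change is that the gap sits in the go/no-go rule, is foreseeable from the section's own survival model, and would cost a sentence to close. Carrying five to 21 or 22 subjects has exact error 5.2% or 6.2%, above the stated 5%, and the plan does not disclose it. Seven responders, where kappa is most sensitive, is also the plan's expected margin.

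Much of this is correct: the definition is missing, the operating characteristics are printed for 20 only, and the error at 21 or 22 is as stated. But the natural remedy, counting the unscanned as non-responders with a fixed five over all treated, changes no verdict and no power figure, and it accepts the same 6.2%. Holding 5% on 22 treated would need six responses, with power 0.84 if all are scanned and 0.75 with 8.9% unscanned. Nor is counting an unscanned man against the scan clearly better: the verdict sentence is about a method of assessment, although Section 7.14 speaks of the efficacy of Ra-223. That is a choice of estimand on which reasonable statisticians differ.

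For kappa, a man without a month-2 scan has no 2-month response status to cross-classify. Leaving him out is the natural reading and agrees with the landmark analysis beside it.

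**Conclusion.** No change follows. Section 8 leaves a definition unwritten, and its own terms lead analysts to a sound answer: count responses among men with both scans, call five or more promising, and tabulate kappa on men who have a response status. The verdict then does not depend on how the unscanned are described.

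What remains is small. If 21 or 22 men are scanned, a fixed five has error 5.2% or 6.2%; averaged over attendance at 91.1%, with 10% as the rate among the scanned, it is 4.4%. A reversed verdict, at 1.8 to 13.2% for the rates shown, needs a cut-off of six that the plan never states. The kappa shift needs 7 or 9 responders within the 3 to 10 range, two deaths and a counting rule that the text does not support.

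The 1.3 to 2.0 deaths assume a constant hazard from a 14.9-month median. The 6-month life-expectancy criterion (Section 5.1.1) and the exclusion of visceral metastases (Section 5.1.2) argue for fewer. The power figures 0.84 and 0.80 rest on an assumed extra loss, and defining the set would not alter them.

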Most bone metastases in men with prostate cancer are characterized by excess bone turnover. Number and activity of both osteoblasts and osteoclasts are increased in typical bone metastases from prostate cancer. Specific biochemical markers of both osteoblast and osteoclast activity are markedly elevated in men with metastatic prostate cancer and levels correspond to extent of skeletal involvement.^{32, 33} In multivariate analyses of data from a large prospective clinical trial of men with CRPC and bone metastases, elevated levels of serum bone specific alkaline phosphatase (BAP), a specific marker of osteoblast activity, was independently associated with shorter overall survival.³⁴ Higher levels of BAP and urinary N-telopeptide (NTx), a marker of osteoclast activity, are associated with greater risk of skeletal morbidity in men with metastatic CRPC. Greater declines in urinary NTx following treatment with zoledronic acid are associated with lower risk of skeletal morbidity in men with metastatic CRPC.³⁵ We hypothesize that Ra-223 treatment will be associated with reductions from baseline in BAP and NTx concurrent with improvement in concurrent assessments by standard and experimental imaging studies.

Biomarkers of Angiogenesis & Inflammation

Biomarkers of inflammation and angiogenesis may substantially improve understanding of Ra-223 activity as well as mechanisms of resistance. In particular, SDF1 α is a chemokine that is highly expressed in the bone marrow and has been shown in preclinical studies to play important roles in tumor growth and resistance to therapy. Malignant cells may use SDF1 α signaling through its receptors CXCR4 and CXCR7 to promote survival and migration. For example, CXCR4 and CXCR7 expression has been associated with decreased cell apoptosis and increased cell proliferation and migration and new vessel formation, including in prostate

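### The analyses of BSA change and survival leave out baseline BSA, so they cannot show whether the 2-month change identifies long-term survivors beyond baseline disease extent

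*Combined protocol and SAP*

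**What the plan says.** Section 8, Secondary Aims, asks whether the quantitative bone scan after 2 months of therapy "can identify patients who will achieve long term clinical benefit". The test is stated as: "A two-sample t-test will be used to determine the difference in mean percent change in BSA between survivor and non-survivor groups". Its power statement reads "There is 80% power to detect an effect of 1.332 SD", "given a 2-sided 0.05 alpha and 20 evaluable patients", split into 9 survivors and 11 non-survivors.

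The same section adds a Pearson correlation of BSA change with survival time, Cohen's kappa, and a landmark analysis at 2 months: "Cox proportional hazards (PH) regression will be used to estimate the bone scan response hazard ratio along with 95% confidence limits". No covariate is named for any of these. Baseline BSA enters only as the reference from which change is computed.

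Three other places bear on the point:

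- Section 7.14 describes BSA as a measure of tumor burden in bone, so baseline BSA is itself disease extent.
- Section 5.1.1 requires at least two skeletal metastases and sets no upper limit, so baseline extent may vary widely.
- Section 1.1 (Bone Turnover Markers) says of bone markers that "levels correspond to extent of skeletal involvement", and reports that raised bone-specific alkaline phosphatase went with shorter survival.

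**The concern.** A 2-month scan helps the clinician identify long-term survivors to the extent that it adds to the screening scan. Two links could blur this. Men with less bone disease may live longer, and percent change may depend on the starting area, since dividing by baseline does not make the change independent of it. If both links hold, the survivor groups differ in mean change even when the change says nothing more about survival once baseline is known.

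The direction is not fixed. If men with small-volume disease shrink proportionally more, the unadjusted result favors BSA change as a marker. If larger baselines show larger percent decreases, as regression to the mean would produce, the unadjusted result runs the other way and can mask a real association. In either case a reader of the planned results could not tell what the change contributes.

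**Working it through.** **Inputs from Section 8.** 20 evaluable men, 9 survivors and 11 non-survivors; two-sided alpha 0.05; 80% power; median survival 14.9 months, exponential; 35% expected responders.

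**Assumed inputs, not in the documents.** Hazard ratio (HR) per SD of baseline BSA 1.5 to 3; correlation of baseline with change between -0.5 and +0.7. A positive sign means that larger baselines shrink less.

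**1. The plan's own figures.** 18-month survival = exp(-ln 2 × 18/14.9) = 0.433, and 20 × 0.433 = 8.7, rounded to 9. For the t-test with 18 df, the noncentrality at 1.332 SD is 1.332 × √(9 × 11/20), which gives power 0.8002. Both figures reproduce.

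**2. Leaving baseline out.** Model: baseline B is standard normal; the hazard is proportional to HR^B, calibrated to 43.3% alive at 18 months; change = ρB + √(1-ρ²) × noise, with no effect on survival given B. At HR 2, mean baseline differs between non-survivors and survivors by 0.856 SD, so mean change differs by 0.5 × 0.856 = 0.43 SD at ρ = 0.5. The response HR column comes from large simulated samples with a 2-month landmark; the rejection rates come from simulated trials of 20.

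| HR per SD | ρ | Difference in mean change, non-survivors minus survivors (SD) | Unadjusted response HR | t-test rejects | Linear model with baseline rejects |
|---|---|---|---|---|---|
| 1.5 | +0.3 | 0.17 | 0.84 | 6% | 5% |
| 2 | +0.5 | 0.43 | 0.62 | 15% | 5% |
| 2 | -0.5 | -0.43 | 1.62 | 14% | 5% |
| 3 | +0.7 | 0.78 | 0.41 | 42% | 5% |
| 2 | 0 | 0.00 | 1.00 | 5% | 5% |

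With baseline in the model, the difference is about 0 and the response HR about 1.0 in every row. With no prognostic effect of baseline (HR 1) the unadjusted analyses also show nothing.

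**3. Cost of adding baseline.** With baseline in the linear model (17 df) and groups balanced on baseline, the effect detectable with 80% power is 1.336 residual SD. If the groups differ by d SD at baseline, r² = (9 × 11/20²) × d² = 0.2475d². If baseline explains a share R² of the variance of change, the detectable effect in SD of change is 1.336 × √(1-R²)/√(1-r²).

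- HR 2, d = 0.856: r² = 0.181. At R² = 0.10: 1.336 × 0.949/0.905 = 1.40 SD. At ρ = 0.5 (R² = 0.25): 1.336 × 0.866/0.905 = 1.28 SD.
- HR 2.5, d = 1.02 (same model, by numerical integration): r² = 0.257. At R² = 0.10: 1.336 × 0.949/0.862 = 1.47 SD.

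Against the planned 1.332 SD, precision can therefore move either way.

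**4. Deaths available to the Cox model.** By 18 months: 20 × (1-0.433) = 11.3. By an assumed 23 months: 20 × (1-exp(-ln 2 × 23/14.9)) = 13.1. With 35% responders, the Schoenfeld formula exp(-(1.960+0.842)/√(D × 0.35 × 0.65)) gives a detectable response HR of 0.17 at D = 11 and 0.20 at D = 13. Power is low with or without adjustment, so what can mislead here is mainly the point estimate.

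**The case against.** The strongest reply is that the plan answers the question it asks. Section 2 words the objective as describing mean change by survival status, and Section 8 asks whether the scan can identify long-term survivors. Both can be read as marginal questions, and an unadjusted comparison answers them validly. This stands. Nowhere do the documents claim that change is informative beyond baseline.

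A reader might infer from the table that the planned t-test has an inflated type I error. It does not. In those scenarios the group means truly differ, so the t-test's own null hypothesis is false and it rejects a real marginal difference. The rates mislead only if the result is read as evidence that the change adds to baseline.

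A reader might also infer that adjustment buys precision and that the t-test should therefore be replaced. The documents do not support this. A gain is assured only if baseline explains variance in change and is not strongly prognostic, and step 3 shows a loss where it is strongly prognostic but weakly related to change.

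Finally, the support is indirect. Section 1.1 links serum markers to extent and one marker to survival; nothing in the documents relates baseline BSA to survival or to percent change. This also stands, and it is why the size is given as a range with both signs. It does not remove the point: Section 8 calls this aim key, gives it a test with alpha and power, and frames it as identifying patients, so incremental readings are likely.

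**Conclusion.** The concern holds as a limit on interpretation. The planned analyses describe the marginal association correctly but cannot say whether the 2-month change identifies long-term survivors beyond baseline extent.

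Under an assumed hazard ratio of 2 per SD and a correlation of +0.5 or -0.5, the unadjusted difference is about 0.43 SD in one direction or the other, and the t-test rejects about 14-15% of the time with no conditional information in the change. The effect vanishes if either relation is zero. No figure stated in the plan is wrong, and the primary endpoint with its rule of 5 responses in 20 is unaffected. The study is small and exploratory, so this is a worthwhile, inexpensive improvement and not a flaw that invalidates the plan.

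**What to change.** Keep the two-sample t-test and the unadjusted landmark hazard ratio as planned. Before the survival data are analyzed, add to Section 8:

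- a linear model of percent change in BSA on 18-month survivor group plus log baseline BSA;
- the 2-month landmark Cox model with bone scan response and log baseline BSA, the latter as the only added covariate;
- the correlation of baseline BSA with percent change, with its sign;
- a sentence that any statement that the 2-month change adds information will rest on the adjusted results.

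The cost is wording and one degree of freedom; every man with a computable change already has the baseline value. If baseline is strongly prognostic but weakly related to change, the adjusted comparison loses some precision: a detectable effect of about 1.40-1.47 SD against 1.332 SD at R² = 10% and hazard ratios of 2-2.5. About 11-13 deaths will support one added covariate in the Cox model but not several, and its interval will be wide. The plan should not present the adjustment as a gain in precision.
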